5.2.2 Tumour Biopsy

Up to 2 mandatory fresh tumour biopsies will be collected for assessment of tumour biomarkers (CAFs, CD8⁺ TILs, regulatory T-cells, and PD1-L1) and gene expression analysis.

Tumour biopsies can be taken from primary tumour site, involved lymph node or metastasis site. Any decision to perform the on-treatment biopsy must consider the patient's condition at that time point, and not be done if the risk to the patient appears unacceptable. Investigators must ensure appropriate clinical judgment is applied when considering whether to perform tumour biopsies as this is a surgical procedure that may not intrinsically benefit individual patients but may benefit medical research.

The first biopsy will be collected during or within 30 days prior to the Screening Period and will be used to determine the CPS score and CAFs level in tumour tissue as part of eligibility criteria, in case no archival tissue was available. Other assessments will include:

- Levels of PD-L1 expression in tumour tissue using the PD-L1 IHC 22C3 pharmDx assay (Agilent), a qualitative immunohistochemical assay using monoclonal mouse anti-PD-L1 clone 22C3 intended for use in the detection of PD-L1 protein in formalin-fixed, paraffin-embedded non-small cell lung cancer, gastric or gastroesophageal junction adenocarcinoma, oesophageal squamous cell carcinoma, cervical cancer, urothelial carcinoma, SCCHN, and triple-negative breast cancer tissues, using EnVision FLEX visualisation system on Autostainer Link 48
- Number of CD8⁺ TILs and regulatory T-cells in tumour tissue
- RNA sequence analysis

To be considered suitable for initial determination of CAF levels, archival tissue biopsy material must have been collected within 6 months prior to the Screening Visit, and the
patient must have received no further anti-cancer therapy since then. To be considered suitable for full Baseline (pre-treatment) biomarker assessment, tumour biopsy specimens must have been collected within 30 days prior to Screening. Samples may be from the primary SCCHN site, regional lymph node, or metastatic site.

Tumour sample may be from either a surgical resection or core needle biopsy or collected as an excisional or incisional tumour biopsy from either the primary or metastatic site during surgery or interventional procedure. Fine needle aspirates are not acceptable. Formalin-fixed paraffin-embedded needle core biopsies may have been obtained via direct visualisation of tumour, or with CT, fluoroscopy, or ultrasound image guided needle biopsy procedures. The tissue cores should have been obtained by the use of an 18 gauge (or larger core diameter) biopsy needle. If smaller needle is used, then additional biopsy cores are to be provided in the block. 10% Neutral buffered formalin is recommended as the tissue fixative.

Samples meeting any of the criteria below are not acceptable:

- Archived tissue with limited tumour content: preferably at least 30% of viable tumour cells
- Cytology samples and fine needle aspirates
- Tissues fixed with other unacceptable fixatives, including 95% alcohol, alcohol formalin acetic acid, and PREFERTM
- Specimens from bone lesions are generally not acceptable unless there is significant soft tissue component or there is no bone tissue in the biopsy

The second biopsy (mandatory for all patients) will be performed 9 weeks (± 1 week) after the start of study treatment or earlier if progression occurs before 9 weeks.

A third optional tumour biopsy can be performed at disease progression (only for patients who had their second biopsy at 9 weeks, who consented to having a third sample).

CAFs will identified in formalin-fixed, paraffin-embedded tissue sections using immunohistochemistry for α SMA. CAFs are positive for α -SMA, and tumour stroma will be assessed for CAFs as previously described (Marsh et al 2011). SMA staining and evaluation of CAF scores will be performed by a single pathologist (or a suitably qualified and trained deputising pathologist) at a central laboratory. The semi-quantitative scoring system separates tumours into 3 groups: low (<5% stroma positive), moderate (5 to 50% stroma positive) and high (>50% stroma positive). Patients with tumours containing moderate or high levels of CAFs will be eligible for the study. The tumour samples will be used for analyses of biomarkers related to SCCHN. The biomarker analyses results will be used to explore the potential relationship with setanaxib response and/or disease progression data obtained in this study.

The samples may be analysed as part of a multistudy assessment of genetic factors involved in the response to setanaxib or IMPs of this class to understand study disease or related conditions.

The tumour sample will be collected, processed, stored, sent for central review, and analysed as defined in the central laboratory manual. Refer to the central laboratory manual for further details.

5.2.3 Peripheral Blood for Circulating Biomarkers Analysis

Blood samples (20 mL whole blood) will be collected for analysis of exploratory circulating biomarkers, before commencing study treatment, during treatment and at progression, as outlined in Table 1. The blood samples will be used for analyses of circulating biomarkers related to SCCHN. The results of biomarker analyses will be used to explore the potential relationship with setanaxib response and/or disease progression data obtained in this study. Samples collected before treatment will be analysed for predictive biomarkers of response to treatment and may be used to develop future in vitro diagnostic tests. Samples collected during treatment and at progression will be used for additional exploratory research which may include but is not limited to interrogation of changes in genetic expression and potential mechanisms of resistance to treatment. A range of oncology and immunological biomarkers that may corelate with drug response will be examined; these may include but are not limited to panels of cytokines, chemokines and other soluble biomarkers associated with immunomodulatory effects.

The samples may be analysed as part of a multistudy assessment of genetic factors involved in the response to setanaxib or IMPs of this class to understand study disease or related conditions.

The blood samples will be collected, processed, stored, sent for central review, and analysed as defined in the central laboratory manual. Refer to the central laboratory manual for further details.

5.3 Safety Assessments

5.3.1 Adverse Events

AEs will be followed, recorded, and reported in line with the procedures described in Section 7. AESIs are defined in Section 7.1.5.

Particular attention will be given to the detection and management of potential cases of anaemia (Section 5.3.2.1), or potential cases of hypothyroidism (see Section 5.3.2.2).

5.3.2 Clinical Laboratory Evaluations

Laboratory assessments will be performed by a central laboratory, unless otherwise specified. The central laboratory will analyse the samples or send them to reference laboratory(ies) for analysis, as indicated in the central laboratory manual. Laboratory assessments of PK are described in Section 5.4.

Blood and urine samples will be collected pre-dose at the times indicated in Table 1. Repeat or unscheduled samples may be taken for safety reasons or for technical issues with the samples. The blood volumes to be collected per patient during the study will be provided in the informed consent form (ICF) and/or in the central laboratory manual. For further details, refer to the central laboratory manual.

Sampling for the analysis of clinical laboratory parameters will be performed before the administration of IMP.

The following parameters will be assessed:

Haematology: haematocrit, haemoglobin, absolute and relative reticulocyte counts, red blood cell (RBC) count, white blood cell (WBC) count, differential WBC count, platelet count, absolute neutrophil count, mean cell volume, and international normalised ratio (INR only at Screening)

Biochemistry: ALP, ALT, AST, amylase, total and conjugated bilirubin, GGT, glucose, total protein, albumin, creatinine, urea, total cholesterol, triglycerides, sodium, potassium, and chloride

Thyroid function test: TSH and free T4

Pregnancy test (serum): See Section 5.3.3.

Urinalysis: qualitative tests will be performed using urine dipsticks (refer to the central laboratory manual for more details)

Pregnancy test (urine): See Section 5.3.3.

In case the HPV status is not known or not documented in the medical records, HPV status will need to be determined before randomisation as per site standard operating procedures (eg, p16 immunohistochemistry or HPV DNA detection [PCR or in situ hybridisation]). The methodology used for HPV testing will be recorded in the eCRF.

Refer to the central laboratory manual for details regarding the collection, processing, and shipping of the blood and urine samples.

The investigator must review the laboratory report, document this review, and record any clinically relevant changes occurring during the study in the AE section of the eCRF. The laboratory reports must be filed with the source documents. Clinically significant abnormal laboratory findings are those that are not associated with the underlying disease, unless judged by the investigator to be more severe than expected for the patient's condition.

All laboratory tests with values considered clinically significantly abnormal during the patient's participation in the study or within 28 days after the last dose of IMP, whichever is later, should be repeated until the values return to normal, to Baseline levels, or have stabilised and are no longer considered clinically significant by the investigator or medical monitor.

If such values do not return to normal/Baseline within a period of time judged reasonable by the investigator, then the aetiology should be identified, and the sponsor (or designee) notified.

If required due to Covid-19-related restrictions, laboratory samples to follow up an AE, including the retests for haemoglobin (see Section 5.3.2.1), or TSH and free T4 (see Section 5.3.2.2), may be collected by a qualified healthcare professional at a location other than the study site. For other circumstances pertaining to patient safety during Covid-19-related restrictions, follow-up with the sponsor (or designee).

Laboratory samples taken to follow up an AE, including the retests for absolute haemoglobin, or TSH and free T4 noted above, may be tested locally so that the results are communicated to the investigator's site promptly. If required due to Covid-19-related restrictions, the results of local safety laboratory tests may be provided to the investigator by telephone. Local laboratory results will not be entered into the eCRF. However, where unscheduled central laboratory confirmation is not possible for protocol-specified retests for evaluation of potential anaemia or hypothyroidism, the retest results may be requested.

5.3.2.1 Detection and Management of Anaemia

Particular attention will be given to the detection and management of potential cases of anaemia. In case of Grade \geq 3 severity anaemia, the investigator will instruct the patient to interrupt IMP administration and to return to the study centre within 7 days so that haemoglobin can be retested. If the severity of anaemia is still Grade \geq 3, and if an alternative cause for the anaemia cannot be documented (alternative cause may include the underlying cancer), IMP will not be resumed and will be permanently discontinued. IMP administration will be resumed only if the retest value for haemoglobin is \geq 9 g/dL and an alternative cause for the anaemia can be documented. The patient will continue to be closely monitored (at least weekly) until normalisation of haemoglobin, ie, return to Baseline values.

Anaemia will be reported to the sponsor (or designee) as an AESI, as defined in Section 7.1.5, following the same procedure as for SAEs (Section 7.4).

5.3.2.2 Detection and Management of Hypothyroidism

Particular attention will be given to the detection and management of potential cases of hypothyroidism. In case of TSH ≥ 10 mIU/L, the investigator will instruct the patient to interrupt IMP administration and to return to the study centre within 5 days so that TSH and free T4 values can be retested. If the retest value is ≥ 10 mIU/L and the patient presents with signs and symptoms consistent with hypothyroidism or if overt biological hypothyroidism is confirmed (ie, TSH ≥ 10 mIU/L and reduced free T4), IMP will not be resumed. If drug-induced hypothyroidism is not confirmed, IMP administration will be resumed as per protocol. The patient will continue to be closely monitored by at least their clinical status and TSH/free T4 levels (at least weekly) until normalisation of the TSH and free T4 values, ie, return to Baseline values.

Hypothyroidism will be reported to the sponsor (or designee) as an AESI, as defined in Section 7.1.5, following the same procedure as for SAEs (Section 7.4).

5.3.3 Pregnancy

All patients are required to meet the requirements relating to pregnancy and use of contraception described in the inclusion and exclusion criteria (see Section 4.1 and Section 4.2, respectively). Male and female patients of childbearing potential must receive pregnancy prevention counselling and be advised of the risk to the foetus if they become pregnant or father a child during treatment and for 6 months after the last dose of IMP or pembrolizumab, whichever is the later. Additional medications given during the study may alter the contraceptive requirements. These additional medications may require female patients to use highly effective methods of contraception and/or for an increased length of time. In addition, male patients are also required to use contraception. The investigator must discuss these contraceptive changes with the patient.

For female patients who are considered postmenopausal but have less than 12 months of amenorrhea and who are not on concomitant oestrogen replacement therapy, a high FSH level in the postmenopausal range will be required at Screening. Confirmation with more than one FSH measurement is required.

Serum (beta human chorionic gonadotrophin) or urine pregnancy tests will be performed for female patients of childbearing potential at the time points indicated in Table 1.

Female patients of childbearing potential must have a serum pregnancy test at the Screening Visit. The blood sample for the serum pregnancy test must be taken within 7 days of Day 1. Therefore, if Screening Visit is performed more than 7 days prior to Day 1, the serum pregnancy test must be repeated within 7 days of Day 1. The result must be negative for the patient to be eligible for the study. If the test result is positive,

the patient must be excluded from the study. The serum pregnancy tests will be analysed by the central laboratory. A negative urine pregnancy test result is required at Baseline/Randomisation and at each visit before dosing. Urine pregnancy tests will be analysed locally.

Any pregnancies in female patients and the partners of male patients will be recorded from the patient's inclusion in the study until 6 months after the last dose of IMP or pembrolizumab, whichever is the later. Male patients will be required to inform the investigator if their partner becomes pregnant during the study and for 6 months after the last dose of IMP or pembrolizumab, whichever is the later. The investigator should inform the sponsor (or designee) within 24 hours of learning of the pregnancy or partner pregnancy by completing and submitting a Pregnancy Report Form to the sponsor (or designee) using the contact details provided. (Note: Sites are not required to provide any information on the pregnancy notification form that violates the country or regions local privacy laws).

If a patient becomes pregnant, she will permanently discontinue IMP and attend an EoT Visit as soon as possible and a Safety Follow-up Visit at 28 days after the last dose of IMP, after which the patient will be encouraged to continue study assessments until disease progression.

After obtaining the female patient's signed authorisation for release of pregnancy and infant health information, the investigator will collect pregnancy and infant health information and complete the pregnancy questionnaire for any female patient who becomes pregnant while taking IMP or pembrolizumab through 6 months following the last dose of IMP or pembrolizumab, whichever is the later. This information will be forwarded to sponsor (or designee). Generally, infant follow-up will be conducted up to 12 months after the birth of the child (if applicable).

Any termination of pregnancy will be reported to sponsor (or designee), regardless of foetal status (presence or absence of anomalies) or indication for procedure.

While pregnancy itself is not considered to be an AE or SAE, any pregnancy complication or elective termination of a pregnancy for medical reasons will be reported as an AE or SAE. Abnormal pregnancy outcomes (eg, spontaneous abortion, foetal death, stillbirth, congenital abnormalities, ectopic pregnancy) will be considered SAEs.

Any SAE occurring as a result of a post-study pregnancy which is considered reasonably related to the study treatment by the investigator, will be reported to sponsor (or designee). While the investigator is not obligated to actively seek this information in former study patients, he or she may learn of a SAE through spontaneous reporting.

For any male study patient's partner who becomes pregnant, the investigator will attempt to collect pregnancy information on the male patient's partner while the male patient is in this study until 6 months after the last dose of IMP or pembrolizumab, whichever is the later. The investigator will record pregnancy information on the appropriate form and submit it to the sponsor (or designee) within 24 hours of learning of the partner's pregnancy. The investigator will obtain informed consent from the female partner to collect information about the pregnancy and its outcome. Information on the status of the mother and child will be forwarded to the sponsor (or designee). Generally, infant followup will be conducted up to 12 months after the birth of the child (if applicable). Any termination of the pregnancy will be reported regardless of foetal status (presence or absence of anomalies) or indication for the procedure. Abnormal pregnancy outcomes (eg, spontaneous abortion, foetal death, stillbirth, congenital abnormalities, ectopic pregnancy) will be considered SAEs.

5.3.4 Breastfeeding

Breastfeeding women will be excluded from the study.

5.3.5 12-lead Electrocardiogram

12-lead ECG will be obtained as outlined in Table 1.

At Visit 2 (Study Day 1) and Visit 3, 12-lead ECG will be recorded pre-dose and 2 hours (± 30 minutes) post setanaxib/placebo dosing. From Visit 4 onwards, 12-lead ECG are only required before setanaxib/placebo dosing; additional ECGs may be recorded as clinically indicated.

The ECGs will be conducted in the supine position after 5 minutes' rest.

The ECG tracing printout should be signed and dated by the person who made the interpretation locally (for purposes of patient safety management); the tracing printout will be archived at the study site. The machines will provide heart rate, PR, QRS, QT, and QTc intervals. If the ECG tracing printouts are in a non-archivable quality, including fading ink, a certified copy should be printed, signed and dated by the person who made the copy and labelled "certified copy". Electronically archived ECG tracings are acceptable as source data provided the electronic archival system is validated.

If there is any evidence of the cardiac conditions or abnormalities noted in Section 4.3.1, IMP is to be permanently discontinued.

Further details regarding the ECG assessments are provided in the site operations manual or manual provided by the vendor.

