Patients with recurrent or metastatic SCCHN have a poor prognosis with a median survival of approximately 1 year. Immune checkpoint inhibitors have shown that they can enhance clinical outcomes in this disease setting and are well tolerated, but only a minority of patients (~20%) show a response to treatment. Increasing response to immune checkpoint inhibitors represents a major challenge, and there is a high unmet medical need for safe and efficacious treatment options in this disease setting. The addition of setanaxib therapy to pembrolizumab may enhance the ability of CD8⁺ T lymphocytes to reach and infiltrate the tumour and thereby increase the degree of response to pembrolizumab, thus increasing the proportion of patients who respond to pembrolizumab therapy, and thereby delaying the onset of disease progression and increasing OS.

Participation in this study provides the patient with a standard-of-care treatment option in the form of the approved agent pembrolizumab, and a potential opportunity to take setanaxib, which is being evaluated for efficacy in this clinical study. While NOX1/4 inhibition represents an attractive therapeutic strategy, therapeutic benefits in patients with SCCHN have yet to be demonstrated. During this study patients will undergo the regular medical evaluations and assessments for their cancer, as part of the study procedures.

Potential Risks

As summarised in Section 1.1.2, setanaxib has been extensively investigated in nonclinical and clinical studies.

In the completed Phase 1 and Phase 2 studies, the safety profile of setanaxib has been shown to be acceptable, with no clinical safety signal and no dose limiting toxicity identified. The safety signals identified in the toxicology studies (thyroid function, electrocardiogram [ECG] abnormalities, haematological changes) have been carefully monitored in all clinical studies completed to date. No treatment-related clinical or pathological findings have been observed, irrespective of dose, treatment duration or type of clinical study.

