- 13. Known human immunodeficiency virus (HIV) infection or acute or chronic hepatitis B or C infection. Patients with a past or resolved hepatitis B virus infection (defined as the presence of hepatitis B core antibody [HBcAb] and absence of hepatitis B surface antigen [HBsAg]) are eligible provided the hepatitis virus DNA test is negative.

Patients positive for hepatitis C antibody are eligible only if polymerase chain reaction (PCR) is negative for hepatitis C virus RNA. Patients with ongoing anti-viral therapy with potent inhibitors of CYP3A4 are not eligible. Testing for HIV is only required if clinically indicated and is not mandatory for this study.

- 14. Serious chronic gastrointestinal conditions associated with diarrhoea.
- 15. History of significant haematological problems, such as blood dyscrasias requiring treatment, aplastic anaemia, myelodysplastic syndrome, or leukaemia.
- 16. Surgery (eg, stomach bypass) or medical condition that might significantly affect absorption of medicines (as judged by the investigator).
- 17. A positive pregnancy test or breastfeeding for female patients.
- 18. Evidence of any of the following cardiac conduction abnormalities: a QTc Fredericia interval >450 milliseconds for male patients or >470 milliseconds for female patients. Patients with a second- or third-degree atrioventricular block are to be excluded.
- 19. TSH >ULN at Screening.
- 20. Unstable cardiovascular disease as defined by any of the following:
 - a. Unstable angina within 6 months prior to Screening
 - b. Myocardial infarction, coronary artery bypass graft surgery, or coronary angioplasty within 6 months prior to Screening
 - c. Cerebrovascular accident within 6 months prior to Screening
 - d. New York Heart Association Class III or IV heart failure
- 21. Presence of any laboratory abnormality or condition that, in the opinion of the investigator, could interfere with or compromise a patient's treatment, assessment, or compliance with the protocol and/or study procedures.
- 22. Any other condition that, in the opinion of the investigator, constitutes a risk or contraindication for the participation of the patient in the study, or that could interfere with the study objectives, conduct, or evaluation.
- 23. Use of medications known to be potent CYP3A4 inhibitors or inducers, or potent uridine diphosphate (UDP)-glucuronosyltransferase 1A9 (UGT1A9) inhibitors or inducers, within 21 days prior to IMP administration.

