4.3.1 Premature Discontinuation of Investigational Medicinal Product

Patients should discontinue the IMP if any of the following occurs:

- 1. The patient withdraws his/her consent to participate in the study.
- 2. The patient develops an illness that would interfere with his/her continued participation in the study, at the investigator's discretion.
- 3. The patient is noncompliant with study procedures or medication, that in the opinion of the investigator, impacts patient safety and/or the integrity of the study results.
- 4. The patient takes a prohibited medication that warrants the IMP discontinuation at the discretion of the investigator (see Section 6.7).
- 5. The patient is confirmed to be pregnant.
- 6. The sponsor or regulatory agency requests withdrawal of the patient.

- 7. The patient is withdrawn for safety reason per the investigator's judgment.
- 8. IMP rechallenge results in anaemia or hypothyroidism IMP interruption criteria being met again (see Section 6.4.2).

At the time of premature IMP discontinuation, the patient should complete the assessments indicated at the EoT Visit (see Table 1). The patient will also be required to attend a Safety Follow-up Visit at 28 days after the last IMP dose. In addition, patients who discontinue study treatment prior to radiological progression will continue to be followed for tumour assessments until RECIST v1.1-defined disease progression, and for survival.

Patients who withdraw consent should be asked whether they would still allow contact for determination of survival follow-up. If patients consent to survival follow-up, they will be withdrawn from study treatment and other study procedures but are not considered to have withdrawn from the study.

Patients who discontinue IMP prematurely will not be replaced.

For details of permitted IMP dechallenge and rechallenge, see Section 6.4.2.

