6.4.1 Dose Modification

Dose interruptions are required in case of anaemia and hypothyroidism, when the events meet the criteria as defined in Section 5.3.2.1, and Section 5.3.2.2, respectively. Events that require permanent discontinuation of IMP are listed in Section 4.3.1.

Dose reduction of setanaxib to 400 mg BID to manage anaemia, hypothyroidism, or any Grade 3 or otherwise intolerable toxicity, which is considered related to setanaxib may be instituted at the investigator's discretion after discussion with the medical monitor.

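### Protocol 5.3.5 makes permanent discontinuation mandatory for cardiac findings listed in Section 4.3.1, but that list has no cardiac item, so the ECG stop rule has no trigger

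*Protocol*

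**What the plan says.** The ECG rule in Protocol Section 5.3.5 is mandatory and takes its criteria entirely from another section: "If there is any evidence of the cardiac conditions or abnormalities noted in Section 4.3.1, IMP is to be permanently discontinued". The section it points to opens with "Patients should discontinue the IMP if any of the following occurs" and then gives eight numbered reasons. Section 6.4.1 confirms that this is the definitive list: "Events that require permanent discontinuation of IMP are listed in Section 4.3.1".

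Section 6.4.1 also permits reduction to 400 mg BID for anaemia, hypothyroidism or "any Grade 3 or otherwise intolerable toxicity, which is considered related to setanaxib may be instituted at the investigator's discretion". That sentence goes on to require discussion with the medical monitor first.

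The only QTc limit in the protocol is exclusion criterion 18 in Section 4.2, "a QTc Fredericia interval >450 milliseconds for male patients or >470 milliseconds for female patients", which also excludes second- and third-degree atrioventricular block. It is an entry criterion. On treatment, Section 5.3.5 says only this about measurement: "The machines will provide heart rate, PR, QRS, QT, and QTc intervals". It names no correction formula.

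**The concern.** ECG abnormality is one of the three preclinical signals that the protocol itself singles out. Section 1.3 says of earlier studies: "The safety signals identified in the toxicology studies (thyroid function, electrocardiogram [ECG] abnormalities, haematological changes) have been carefully monitored". Table 2 records QT prolongation and atrioventricular block in dogs at high doses. Section 3.2 accepts human exposures near the NOAEL at 800 mg BID partly because the signals that define the NOAEL can be followed in the clinic. That argument needs an ECG result to lead to a defined action.

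The authors evidently meant it to, because Section 5.3.5 orders a permanent stop. If the cross-reference leads to no cardiac criterion, an investigator with an abnormal tracing cannot tell from the protocol whether the mandatory rule applies. Two sites could then treat the same finding differently, and both would be following the text.

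**Working it through.** No arithmetic is involved. The check is to follow the reference, classify what is there, and then look for the criterion elsewhere.

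**Step 1. The list in Section 4.3.1.** The items run from 1 to 8 without a gap:

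1. consent withdrawn
2. illness that interferes with participation, at the investigator's discretion
3. noncompliance
4. prohibited medication
5. pregnancy
6. request by the sponsor or a regulator
7. safety, in the words "The patient is withdrawn for safety reason per the investigator's judgment"
8. interruption criteria for anaemia or hypothyroidism met again on rechallenge

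Items naming a cardiac condition, an ECG abnormality or a QTc value: 0 of 8. Items 2 and 7 are broad enough to cover an ECG finding, but they carry no limit and rest on judgment. Item 8 is the only one tied to named toxicities, and neither is cardiac.

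**Step 2. Other places where a criterion might be.**

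- Protocol 4.2, exclusions 18 and 20: cardiac criteria, but for entry. Section 5.3.5 does not cite them.
- Protocol 6.4.1: interruption is mandatory only for anaemia and hypothyroidism. For permanent stops it refers back to Section 4.3.1.
- Protocol 3.4: recruitment pauses for related fatal events or for unexpected, related life-threatening events. It has no ECG limit and no rule for the individual patient.
- Protocol Table 2: lists regular ECG monitoring as mitigation and gives no action limit.
- SAP 10.11 and 12.6.5: QTcF bands up to >500 ms, and change bands up to >60 ms, used for summaries. No action is attached.
- The site or vendor manual mentioned in Section 5.3.5: not available, and cited for details of the ECG assessments. The stop rule itself cites only Section 4.3.1.

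On-treatment ECG stop criteria found: none.

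**Step 3. The three signals side by side.**

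| Signal | Action limit on treatment | Required action | Section |
|---|---|---|---|
| Anaemia | Grade ≥3 | Interrupt and retest within 7 days; permanent stop if still Grade ≥3 with no documented alternative cause | 5.3.2.1 |
| Hypothyroidism | TSH ≥10 mIU/L | Interrupt and retest within 5 days; not resumed if TSH is still ≥10 mIU/L with clinical signs and symptoms or reduced free T4 | 5.3.2.2 |
| ECG abnormality | None stated | Permanent stop, by reference to a list with no cardiac item | 5.3.5 |

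**Step 4. What was probably meant.** The subject matter of the Section 5.3.5 rule resembles exclusions 18 (conduction abnormalities) and 20 (unstable cardiovascular disease), so the section number may simply be wrong. A list of cardiac items may instead have been dropped from Section 4.3.1. The documents do not settle which. A slip in numbering is plausible, because item 4 of the same list cites Section 6.7 for prohibited medication, whereas the prohibited drugs are in Section 6.8.

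**The case against.** The strongest reply is that a broken reference does not leave patients unprotected. Items 2 and 7 of Section 4.3.1 let an investigator stop IMP for any ECG finding. ECGs are recorded at every treatment visit and read locally for patient safety. ECG abnormalities with signs or symptoms are recorded as adverse events when they meet that definition (Section 7.1.4). An unblinded IDMC reviews safety and may recommend a change of dose (Section 9.4). Dose reduction under Section 6.4.1 needs a discussion with the medical monitor, so it is not left to the site alone. Table 2 also reports no hERG effect and no clinically relevant ECG change in clinical studies, and Appendix III rates the QT risk as low.

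All of that stands, and it limits the point. A reader might infer that nothing would stop dosing in a patient with marked QT prolongation; the layers above do not support that. What the reply does not supply is the trigger that Section 5.3.5 promises. A rule requiring a permanent stop for named conditions is not met by a clause that leaves the decision to judgment.

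A reader might also try to count the permanent stops that would follow if sites borrowed the entry limits of 450 and 470 ms. The documents give no QTcF mean, no between- or within-patient SD and no drug effect in this population. Nor does anything in them tell a site to stop a patient permanently on one unconfirmed ECG above an entry limit. Any such count would rest on assumptions from outside the documents.

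Finally, the SAP is written against protocol v5.0 (12 December 2023), and only Version 4.0 was available. A correction in v5.0 is possible.

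**Conclusion.** The point holds for Protocol Version 4.0 and the SAP: 0 of 8 items in the cited list are cardiac, and neither document states an on-treatment ECG stop criterion. The mandatory rule in Section 5.3.5 therefore cannot operate as written, and only discretion remains for a signal that the protocol names and relies on monitoring to contain. This is wrong as written, not merely thin on detail, and it should be corrected.

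Its reach is limited. It is an inconsistency in safety conduct. A reader might infer a defect in the primary analysis, but the documents do not show one: SAP 9.1.1 already says how data after premature treatment discontinuation are used, and no test or derivation depends on the ECG rule. The conclusion rests on no numerical assumption. It depends only on the versions available and would lapse if v5.0 already repairs the reference.

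**What to change.** Make the rule executable in one of two ways:

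- add the intended cardiac criteria to Section 4.3.1 as a new item 9; or
- correct the reference in Section 5.3.5 to the criteria that were meant, possibly exclusions 18 and 20 in Section 4.2. These would need rewording as new on-treatment events, since most of exclusion 20 is framed as a six-month look-back before Screening.

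Either way, the criteria should cover at least new second- or third-degree atrioventricular block and a stated QTcF limit confirmed on a repeat ECG. Section 5.3.5 should name the Fridericia correction, which exclusion 18 and the SAP already use. A QTcF >500 ms or an increase >60 ms from Baseline is one reasonable choice. These are the top bands in SAP 10.11, but those bands are descriptive there and do not show what the sponsor intended. The sponsor should set the final limits.

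Section 6.4.1 should say whether reduction to 400 mg BID, after discussion with the medical monitor, is available for these events or whether they always require a permanent stop. If v5.0 already contains the correction, no further change is needed beyond checking that Sections 4.3.1, 5.3.5 and 6.4.1 agree.

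The cost is a short protocol amendment and a repeat ECG for the occasional patient who crosses a limit. No scheduled visit or assessment is added.
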